#### 1.4 Preliminary Data

[figure not shown]
Our research group focuses on using dietary interventions, primarily dietary fiber supplementation, to restore and maintain a healthy gut microbiota as a key strategy to improve metabolic health. In a cohort of children with Prader-Willi syndrome (a genetic form of obesity) (6), we showed that a diet enriched in non-digestible carbohydrates induced significant weight loss and metabolic improvements, an effect associated with structural changes of the gut microbiota. Importantly, germ-free mice that received fecal microbiota transplantation derived from participants post-intervention exhibited a more favorable metabolic profile and glycemic control as compared to those animals that received pre-intervention fecal material, which provided direct evidence for the gut microbiota to causally contribute to the host glucose homeostasis.

In two cohorts that we have recently completed, a comparable 3-month high dietary fiber regimen was able to significantly reduce HbA1c in adults with type 2 diabetes (under review with *Nature*). Below are the HbA1c data from the GUT2D (participants were institutionalized; Figure 2A) and the QIDONG studies (participants were under free-living conditions; Figure 2B).

**Figure 2. The effects of a high dietary fiber regimen on HbA1c in patients with type 2 diabetes in the GUT2D (A) and QIDONG (B) cohorts.**

In the GUT2D cohort, high dietary fiber intake induced shifts in the overall structure of the gut microbiota (Figure 3A) that was driven by an increased abundance of a guild of acetate- and butyrate-producing bacteria (Figure 3B). The dramatic reduction of fecal pH from  $6.82 \pm 0.07$  at baseline to  $6.36 \pm 0.11$  at the end of the 3-month intervention, together with trended increase in overall fecal SCFA content, supported that a high dietary fiber regimen was effective in increasing bacterial carbohydrate fermentation, and these were associated with improvements in glucose homeostasis and overall metabolic profiles of patients with type 2 diabetes.

**Figure 3. Changes in the overall gut microbial structure (A) and the guild of short-chain fatty acid producers promoted by the high dietary fiber intervention (B). U = control group and W = high dietary fiber group.**

### 1.5 Sample Size Justification

No power calculation is performed for this pilot study. We aim to have 5 completers in the Non-Diabetes and 5 in the Prediabetes/Diabetes group, for each of the test panel (i.e. a total of 20 completers). This sample size is comparable to those used in published pilot studies on bran products. Steinert et al (7) used 10 participants (healthy, overweight and obese) to examine the effect of oat bran on glycemic response; Sheflin et al (8) used 7 participants (3 in control and 4 in experimental group) to examine the effect of heat-stabilized rice bran on gut microbiota and metabolites.

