#### **A. Objectives**

To characterize the effect of food supplemented with dietary fiber on postprandial blood glucose levels. This pilot study will generate data to facilitate the development of a high dietary fiber dietary intervention for an upcoming study that aims at improving gut microbial profile and functions to improve glycemic control in patients with type 2 diabetes.

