**GROUP ASSIGNMENT.** Upon confirmation of eligibility, the Research Officer will measure fasting blood glucose concentration (FBG) by performing a finger prick test (ACCU-CHEK® Aviva Plus, Roche Diabetes Care, Indianapolis, IN). Participants who are clinically diagnosed with impaired glucose tolerance or type 2 diabetes (diet-controlled and/or on oral hypoglycemic medications) will be assigned to the Prediabetes/Diabetes group irrespective of their finger prick test results. For participants who are not diagnosed with diabetes, those with FBG < 100 mg/dL will be assigned to the Non-Diabetes group, and those with FBG ≥ 100 mg/dL will be assigned to the Prediabetes/Diabetes group based on classification guidelines from the American Diabetes Association (5). Participants will also be asked to sign up for one of the testing panels: 1) Panel A will test one control food (white bread) and six fiber-supplemented food (dietary fiber mix in water, hot waffle, room temperature waffle, hot pancake, room temperature pancake and muffin); or 2) Panel B will test one control food (white bread) and six fiber-supplemented food (dietary fiber mix in water, sponge cake, crispbread, vegetable smoothie, fruit smoothie and muffin). Finally, the Research Officer will collect information to complete the participant profile, including anthropometry measurements (height and weight), and demographics and contact details.

The eligibility screening and group assignment visit will take approximately 1 h to complete.

**FOOD TESTING.** In the morning of each testing day, participants will attend IFNH between 8 and 10 am after an overnight fast of at least 8 h. They will be required to consume all the study food provided under supervision. The

amount of white bread to be consumed will contain 50 g of available carbohydrates (3-4 slices of bread), and the amount of fiber-supplemented food to be consumed will contain 60 g of dietary fiber mix (approximately 2 waffles, 2 pancakes, 2 slices of sponge cake, 2 serves of crispbread, 2 muffins or 300 ml of smoothies). Participants may leave the research facility after consuming the food, and they will be instructed to refrain from eating and drinking (except water) for the next 3 h. Each food will be tested twice over two consecutive days, with all testing to be completed in 4 weeks (Figure 1). Each food testing session will take approximately 30 min to complete.

[figure not shown]

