**C. Require Number of Subjects to Complete Research**

20 (5 each in Panel A Non-Diabetes group and Prediabetes/Diabetes group, same two groups for Panel B)

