**D. Feasibility Of Recruiting**

We expect to recruit the majority of our participants from the New Brunswick campus of Rutgers University. With a relatively flexible study schedule and no particularly stringent eligibility criteria, we do not anticipate difficulties in engaging interest in the Rutgers community. We expect a recruitment rate of 4-6 participants per week over 4-6 weeks including an estimated attrition rate of 20%.

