**6.0 Research Data Protection and Reporting**

**6.1 Data Management and Confidentiality**

**A. Data analysis plan:** Statistical analyses will be performed using the SPSS Statistics Software Package. Analysis of variance with Tukey's post-hoc test (two-tailed) will be used for intra-and inter-group comparisons of postprandial blood glucose concentration (area-under-curve). Independent-samples *t* test (two-tailed) will be used to analyze variations in other participant characteristics. Statistical significance will be accepted at *p* value < 0.05.

**B. Quality control:** All research personnel will complete CITI training and be knowledgeable about Good Clinical Practice (GCP), relevant regulations and policies. The Principal Investigator will ensure adherence to the study protocol, regulatory requirements, GCP standards at all times. Team meeting will be held on a regular basis to review adherence to study protocol, and to discuss any incidents of failures of protocol compliance, keeping adequate and accurate records, and reporting of adverse events.

**C. Data handling:** The study data will include two key components: 1) a master code identifier that contains the personal information of the participants and the participant code assigned to them; and 2) study data files that contain all the de-identified data generated in this trial. Participants' hard copy files will be kept in locked cabinets only accessible by authorized research personnel in a secured building. Electronic files will be password-protected and stored on the university's secure server and will only be accessible to authorized research personnel. The master code identifier and the data files will be kept in two separate locations. The master code identifier is only accessible to the Principal Investigator, Study Physician and research staff who schedule appointments and the study data files are accessible to authorized research personnel who work in relevant components of the trial. Data in hard copies and the master code identifier will be kept for 6 years after study completion, thereafter they will be shredded. As data will then exist in de-identified form, the electronic data files will be kept indefinitely. The Principal Investigator will be responsible should receipt and/or transmission of data is required. All data transported/shared will be de-identified.

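### The pilot is meant to supply data for a later study, but its only stated AUC analysis is a significance test: Section 6.1 A should make estimates, intervals and variance components the main output

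*Combined protocol and SAP*

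**What the plan says.** All references are to the combined protocol and SAP.

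- **Aim (Section 1.1 A):** to characterize the effect on postprandial glucose. It adds "This pilot study will generate data to facilitate the development of a high dietary fiber dietary intervention for an upcoming study".
- **Size (Section 1.5):** "No power calculation is performed for this pilot study". The target is stated as "We aim to have 5 completers in the Non-Diabetes and 5 in the Prediabetes/Diabetes group, for each of the test panel", 20 in total, and is supported only by likeness to two small published pilots. Section 4.5 C repeats the same cells.
- **Replication (Section 1.3, Food Testing):** "Each food will be tested twice over two consecutive days". Each participant tests six fiber foods and white bread.
- **Analysis (Section 6.1 A):** "Analysis of variance with Tukey's post-hoc test (two-tailed) will be used for intra-and inter-group comparisons of postprandial blood glucose concentration (area-under-curve"). The criterion follows: "Statistical significance will be accepted at" p < 0.05.

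Section 6.1 A does not say whether the ANOVA is repeated-measures, whether groups are analysed separately or pooled, or how the two tests of a food enter the analysis. Nowhere do the documents plan a mean difference, a confidence interval or an SD for AUC.

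**The concern.** The stated purpose and the stated output do not match. A study that makes no claim to power and exists to inform a later one needs to deliver the size of each food's effect, how uncertain that size is, and how much AUC varies within and between people. A significant/not-significant result delivers none of these.

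In a small sample it can also mislead in both directions. A moderate effect can easily fail to reach significance and be taken for no difference from bread. An effect that does reach significance has had to clear a high threshold, so on average it is overestimated. The duplicate tests could give a usable within-person SD with no further visit, but the plan does not say that one will be reported.

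**Working it through.** **Inputs from the documents.** 5 completers × 2 glycemic groups × 2 panels = 20, which agrees with Sections 1.5 and 4.5 C. Each person tests 7 foods, twice each (Section 1.3). The test is Tukey, two-sided, at 0.05 (Section 6.1 A). There is no stated power to reproduce.

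**Inputs assumed.** The documents give no effect size and no AUC SD. I take a within-person CV of 20/25/30% of bread AUC, the same absolute SD for every food, duplicates averaged, no person-by-food variation, a within-person analysis, and Tukey over the 7 foods of one panel. The within-person analysis and the absence of person-by-food variation favour the plan.

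**Standard error of a food-minus-bread difference, % of bread AUC.** SE = (CV/√2) × √(2/n) = CV/√n.
- n = 5 (one group in one panel): 8.9/11.2/13.4
- n = 10 (both groups of a panel): 6.3/7.9/9.5

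**Critical value.** q(0.95; 7, 6(n−1))/√2.
- n = 5, 24 df: 4.541/√2 = 3.21
- n = 10, 54 df: 4.331/√2 = 3.06

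**Smallest observed difference that reaches significance.** Critical value × SE.
- n = 5: 28.7/35.9/43.1%
- n = 10: 19.4/24.2/29.1%

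**Power and average estimate when significant.** Power is from the noncentral t with noncentrality (true reduction)/SE. For example, at n = 5, CV 25% and a true 30%, this is 30/11.18 = 2.68, giving power 0.33. The average estimate among significant results is by simulation. Each entry is for CV 20/25/30%.

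| True reduction | n | Power | Average estimate when significant |
|---|---|---|---|
| 20% | 5 | 0.20/0.10/0.06 | 32/38/44% |
| 20% | 10 | 0.54/0.31/0.18 | 24/29/33% |
| 30% | 5 | 0.56/0.33/0.20 | 36/41/47% |
| 30% | 10 | 0.95/0.76/0.54 | 31/33/37% |
| 50% | 5 | 0.99/0.88/0.69 | 50/52/56% |

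**What estimation would give from the same data.**
- *Paired difference.* The 95% half-width is t(0.975; n−1)/√n times the SD of the person-level differences: 1.24 SD at n = 5 and 0.72 SD at n = 10. Under the assumptions above that SD equals the CV, because (CV/√2) × √2 = CV. The half-widths are then 24.8/31.0/37.2% of bread AUC at n = 5 and 14.3/17.9/21.5% at n = 10. These are wide, but they say so openly.
- *Within-person SD.* Each duplicate pair gives 1 df, so 20 × 7 = 140 df at most. The 95% limits are √(140/174.65) = 0.90 and √(140/109.14) = 1.13 times the estimate. This requires complete duplicates, a common variance across foods and groups, and removal of any systematic shift from the first day to the second.
- *Between-person SD of the difference.* This rests on n−1 df per food, so the SD of the person-level differences has limits of 0.60 to 2.87 times the estimate at n = 5 and 0.69 to 1.83 at n = 10. It is worth reporting, but it is imprecise.

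**The case against.** The strongest reply is that a declared pilot need not be powered, and that the low power figures come from assumed CVs and effects. Much of this stands.

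- The missing power calculation is not a fault. Section 1.5 is open about it.
- A reader might infer that real effects will mostly be missed. The documents do not support that. They give no effect size or SD. At CV 20% a true 30% reduction has power 0.56 even with 5 people, and pooled to 10 it has 0.95/0.76/0.54. Large differences are also plausible: Section 1.3 fixes bread by available carbohydrate but the test foods by fiber mix, and one item is the mix in water.
- Five is the recruitment cell. Section 6.1 A does not confine the AUC test to it. Pooling gives 10 per panel, and up to 20 for white bread, fiber mix in water and muffin, which are in both panels.
- A reader might infer that the duplicates go unused. The plan only leaves their use unspecified. They may be averaged or enter the error term.
- A reader might infer that non-significant foods will be dropped. No selection rule is stated, and nothing says that the later study will be sized from these AUCs.

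What does not stand is that estimates would be reported anyway, since nothing commits the investigators to it. Nor can large effects be counted on for every contrast. Section 1.1 B also expects differences among foods of equal fiber content, from cooking procedure and serving temperature, and the documents give no reason to expect those to be large.

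**Conclusion.** The point holds as a mismatch between purpose and planned output, located in Section 6.1 A rather than in the absence of a power calculation. The AUC plan names only a significance test, although the aim is to characterize effects and inform a later study.

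The size of the consequence is conditional on the assumed CV and true effect. At a within-person CV of 20 to 30%, moderate effects can often be missed and, when significant, overestimated. For a true 20% reduction, power runs from 0.20 down to 0.06 with 5 people and from 0.54 to 0.18 with 10. The average significant estimate is 32 to 44% and 24 to 33% respectively. For effects near 50% the problem is small. If the ANOVA were not within-person, or if foods acted differently in different people, power would be lower than shown.

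The change is worthwhile because it is cheap and fits the stated aim better. No stated decision rule has been shown to fail.

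**What to change.** Amend Section 6.1 A as follows.

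1. Make estimation the primary analysis. For each food, report the mean within-person AUC difference from white bread with its 95% confidence interval, by glycemic group and pooled within panel. Use a repeated-measures or mixed model that includes both replicates, and say how they enter.
2. Report the within-person SD from the duplicates, after removing any systematic shift from the first day to the second, with its confidence interval. State the common-variance assumption, and note that consecutive-day variation need not represent variation over longer periods.
3. Report the between-person SD of the food-minus-bread difference, with its interval.
4. Keep ANOVA with Tukey if wanted, but label its p-values exploratory and state that p ≥ 0.05 will not be read as no effect.

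Section 1.5 can keep its statement that power was not calculated.

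The cost is wording and a few lines of output, with no added participant, visit or measurement. The real concession is that the pilot no longer confirms or refutes the Section 1.1 B hypotheses by p-value.

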### 1.6 Study Variables

#### A. Independent Variables, Interventions, or Predictor Variables

The independent variable will be type of food: white bread vs dietary fiber mix in water, waffle, pancake, sponge cake, crispbread, vegetable smoothie, fruit smoothie and muffin.

**B. Dependent Variables or Outcome Measures**

The outcome measure will be postprandial blood glucose concentration.

**1.7 Drugs/Devices/Biologics**

N/A

**1.8 Primary Specimen Collection**

N/A

**1.9 Interviews, Focus Groups, or Surveys**

N/A

**1.10 Timetable/Schedule of Events**

	Sept 2017	Oct 2017	Nov 2017	Dec 2017	Jan 2018	Feb 2018
Staff/student training, departmental setup, research material development						
Recruitment						
Eligibility screening and group assignment						
Food testing						
Data analyses						
Write up, results dissemination and record archiving						

## 2.2 Resources Available

**FACILITIES.** All procedures will be conducted at IFNH. The Cook-Douglass Student Health Center is equipped with interview rooms for eligibility screening visits. The dietary fiber mix will be prepared at the Food Innovation Center and stored at IFNH until use. Harvest Café will prepare all the test food and provide seating for food consumption.

**GLUCOSE MONITORING DEVICE.** The FreeStyle Pro, the continuous glucose monitoring system, will be purchased from Abbott Diabetes Care. The Abbott technical support team will provide training to the research team on the sensor application and data download procedures, and ongoing technical support throughout the study.

**RESEARCH TRAINING.** All investigators and research personnel will complete the Collaborative Institutional Training Initiative (CITI) training. Those who will work in the clinical research facilities will also be required to complete the Lab Safety/Biological Safety/Blood Borne Pathogens Training from Rutgers Environmental Health & Safety.

## 3.0 Multi-Site Research Communication & Coordination

N/A

## 4.0 Research Data Source/s

### 4.1 Primary Data-Subjects and Specimens

Male and female individuals

### 4.2 Subject Selection and Enrollment Considerations

#### A. Recruitment Details

Recruitment will start in October 2017 (pending IRB approval). Prospective participants will be recruited through advertisements on Rutgers University website and email lists, and flyers on Rutgers University campuses. Interested individuals will be asked to contact the research team by phone, during which a research officer will provide an overview of the study and describe the broad selection criteria. Prospective participants will be invited to attend a screening visit to establish eligibility. The final selection will be

contingent upon the individuals meeting all eligibility criteria and are deemed capable of complying with the intervention protocol.

#### **B. Source of Subjects**

We expect most of the participants will be employees or students of Rutgers University, although we would also anticipate prospective participants from the wider community via word-of-mouth.

#### **C. Method to Identify Potential Subjects**

An advertisement will be placed in the Rutgers University website and email lists (Attachment 3A). Flyers will be posted on the Rutgers University campuses (Attachment 3B).

#### **D. Subject Screening**

Prospective participants will attend an eligibility screening visit at IFNH after an overnight fast of at least 8 h. They will meet a member of the research team who will decide eligibility based on the following criteria:

##### **▪ Inclusion Criteria**

- Aged between 18 and 55 years
- Understand and be able to follow written and oral instructions in English
- Provide written informed consent

##### **▪ Exclusion Criteria**

- Receiving insulin for diabetes treatment
- Receiving injectable prescription medicine
- Self-reported allergy or intolerance to any ingredients in the test food
- Any conditions deemed by the investigators that would prevent participation in the study, e.g. participation in past or active clinical research that may interfere with study outcomes, at the discretion of the investigators
- Any conditions deemed by the investigators that would compromise the individual's ability to complete the study, e.g. serious psychiatric conditions, at the discretion of the investigators

#### **E. Recruitment Materials**

Please see Attachment 3.

#### **F. Lead Site Recruitment Methods**

N/A

#### **4.3 Subject Randomization**

Participants will not be randomized. They will be assigned to the Non-Diabetes group if their FBGs are < 100 mg/dL, and to the Prediabetes/Diabetes group if their FBGs are  $\geq 100$  mg/dL. At participant's choice, they will sign up to one of the two testing panels (see Section 1.3).

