**Figure 1. Study design.**

**RECRUITMENT.** Prospective participants will be recruited through advertisements on Rutgers University website and email lists (Attachment 3A), and flyers on the Rutgers University campuses (Attachment 3B). Interested individuals will be asked to contact the research team by phone, during which a research officer will provide an overview of the study and describe the broad selection criteria. Prospective participants will be invited to attend a screening visit to establish eligibility. The final selection will be contingent upon the individuals meeting all eligibility criteria and are deemed capable of complying with the protocol.

**ELIGIBILITY SCREENING.** Prospective participants will attend the eligibility screening visit after an overnight fast of at least 8 h. They will meet a member of the research team at IFNH, who will provide a detailed description of the study, including the rationale, aim, expected outcomes and significance of the research, the experimental procedures, what is required from the participants, and the benefits and risks associated with the study. Written informed consent (Attachment 4) will be obtained prior to the eligibility screening process. All information collected during the screening process will be documented in the screening checklist (Attachment 7). Specifically a Research Officer will record medical history and current medications and assess eligibility. Patients with type 2 diabetes who are receiving nutritional management and/or oral hypoglycemic medications may be eligible for the study, however those who are receiving insulin treatment or other injectable prescription medication will be excluded. A full list of inclusion and exclusion criteria is available in Section 4.2.

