#### **4.5 Number of Subjects**

##### **A. Total Number of Subjects**

24

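### Sections 1.3 and 4.3 place a diagnosed participant with fasting glucose below 100 mg/dL in different groups; a lesser point is that 24 enrolled at 20% attrition gives 19.2 expected completers, not 20

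*Combined protocol and SAP*

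**What the plan says.** **Grouping.** Section 4.3 states a two-way rule on FBG with no exception for a diagnosis: "They will be assigned to the Non-Diabetes group if their FBGs are < 100 mg/dL", and Prediabetes/Diabetes otherwise. It refers to Section 1.3 only in its sentence on choosing a panel.

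Section 1.3 (Group assignment) has two steps. Participants with clinically diagnosed impaired glucose tolerance or type 2 diabetes "will be assigned to the Prediabetes/Diabetes group irrespective of their finger prick test results". The cut-off comes next: "For participants who are not diagnosed with diabetes, those with FBG < 100 mg/dL will be assigned to the Non-Diabetes group", with those at or above 100 mg/dL going to Prediabetes/Diabetes.

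The eligibility text in Section 1.3 allows the disputed case to occur: "Patients with type 2 diabetes who are receiving nutritional management and/or oral hypoglycemic medications may be eligible for the study". The criteria in Section 4.2 set no glucose limit.

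The groups enter the analysis in Section 6.1 A, which plans intra-group and "inter-group comparisons of postprandial blood glucose concentration (area-under-curve").

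**Numbers.** Section 1.5 says "We aim to have 5 completers in the Non-Diabetes and 5 in the Prediabetes/Diabetes group, for each of the test panel". Under "Total Number of Subjects", Section 4.5 A gives 24. Section 4.5 C, whose heading asks for the number required to complete, answers "20 (5 each in Panel A Non-Diabetes group and Prediabetes/Diabetes group, same two groups for Panel B"). Section 4.5 D estimates attrition at 20%.

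**The concern.** Group membership defines one side of a planned comparison, so it should not depend on which section the staff member at the screening visit happens to follow. The participants affected are those the exception in Section 1.3 was written for: people with a diagnosis whose fasting reading is below the cut-off. If Section 4.3 is followed, they enter the Non-Diabetes group and are analysed there. They also count towards that group's completers, so the error would affect recruitment as well as the comparison.

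Separately, the plan's own attrition figure does not deliver the completers it asks for, and the status of the 5 per cell is unclear. It is an aim in Section 1.5 and a requirement under the heading of Section 4.5 C.

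**Working it through.** **Grouping: the two rules side by side**

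| Participant | Section 1.3 | Section 4.3 |
|---|---|---|
| Diagnosed, FBG ≥ 100 mg/dL | Prediabetes/Diabetes | Prediabetes/Diabetes |
| Diagnosed, FBG < 100 mg/dL | Prediabetes/Diabetes | **Non-Diabetes** |
| Not diagnosed, FBG ≥ 100 mg/dL | Prediabetes/Diabetes | Prediabetes/Diabetes |
| Not diagnosed, FBG < 100 mg/dL | Non-Diabetes | Non-Diabetes |

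The sections disagree in one row only. Nothing in the documents says which section prevails. One affected person in a cell of 5 is 1/5 of that cell.

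There is also a looseness inside Section 1.3. The sentence with the cut-off excludes only people with diagnosed diabetes. By its words it therefore also covers someone with diagnosed impaired glucose tolerance, whom the preceding sentence has already assigned. The preceding sentence settles the case, but the wording should match it.

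**Numbers: inputs** (all Section 4.5): 24 subjects, 20 completers as 5 in each of 4 cells, 20% attrition.

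1. The plan's figure: 20 × (1 + 0.20) = 24. This reproduces the stated total exactly, although the documents do not say it was derived this way.
2. Expected completers: 24 × (1 − 0.20) = 19.2, or 6 × 0.80 = 4.8 per cell with 6 enrolled in each.
3. Enrolment that gives 20 on average: 20 / (1 − 0.20) = 25, one more than stated.
4. Attrition at which 24 gives 20 on average: 1 − 20/24 = 16.7%.

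**Chance of reaching the numbers.** This assumes independent dropout with probability *a*. The last column also assumes exactly 6 enrolled per cell. Neither assumption is in the documents, and the 10% and 25% rows are there only to show the range.

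| *a* | P(at least 20 of 24) | P(at least 5 of 6) | All four cells = fourth power |
|---|---|---|---|
| 10% | 0.915 | 0.886 | 0.615 |
| 20% | 0.460 | 0.655 | 0.184 |
| 25% | 0.247 | 0.534 | 0.081 |

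Participants choose their panel, so the cells may be uneven. At 20% attrition, P(at least 5 of 7) = 0.852 and P(5 of 5) = 0.328.

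- A 7/5 split in one group: 0.852 × 0.328 × 0.655² = 0.120.
- A 7/5 split in both groups: (0.852 × 0.328)² = 0.078.

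**The case against.** **On grouping.** Section 4.3 is a short answer under a form heading about randomization, and its main message is that there is none. Section 1.3 is the working procedure, so Section 4.3 can be read as an incomplete summary. The group is a label: both groups are offered the same panels, foods and monitoring. The hypotheses in Section 1.1 concern food against white bread and the effect of preparation, and the only independent variable in Section 1.6 is type of food. Medical history and medication are recorded, so a misfiled participant could be moved before analysis.

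Much of this stands, and it limits the consequence: the within-participant comparison of foods does not depend on the group label. It does not remove the contradiction. Section 4.3 reads as a complete rule, its cross-reference does not attach to that rule, and no reclassification step is planned. Moving one person after recruitment would also turn cells of 5 and 5 into 4 and 6.

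**On numbers.** The shortfall is less than one person in a pilot without a power calculation. The word for required comes from the form's heading, while the investigators' own prose says aim. Section 4.5 D attaches the 20% to a recruitment forecast of 4–6 per week over 4–6 weeks (16 to 36 people), so its link to 24 is inferred. It can also be said that stating 19 while keeping a target of 20 leaves a gap. All of this is fair and is why the point is minor. The three figures still sit together in Section 4.5 and do not agree, and a target that is openly above the expected number is clearer than a requirement that the plan's own attrition rate does not meet.

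**Conclusion.** Both points hold.

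The grouping contradiction is the one that matters. It follows from the text and needs no assumption. It affects only diagnosed participants with FBG below 100 mg/dL. The documents do not say how many to expect, and neither the size nor the direction of any effect on the between-group comparison can be determined from them. The figure of a fifth of a cell applies if one such person enrols.

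The attrition point is minor: 0.8 of an expected completer overall. The 46% chance of at least 20 completers rests on independent dropout at 20%. The 18% chance of filling every cell also rests on 6 enrolled per cell, and it falls to 12% or 8% under the uneven splits shown.

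The text should be corrected before enrolment.

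**What to change.** 1. Reconcile Sections 1.3 and 4.3 and use one identical grouping text in both. The sponsor must say which rule is intended. If it is the one in Section 1.3, copy it to Section 4.3 and reword the sentence with the cut-off so that it applies only to people with neither diagnosed impaired glucose tolerance nor diagnosed diabetes.
2. In Section 4.5, state 24 enrolled with about 19 expected completers, and describe 5 per cell as a target, in line with Section 1.5.
3. Optionally, cap sign-up at 6 per group-by-panel cell (4 × 6 = 24). This prevents uneven splits but does not make 5 per cell secure: the chance stays at 18% under the assumptions above.

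Items 1 and 2 cost only text edits to Sections 1.3, 4.3 and 4.5; the enrolled total, visits and analysis are unchanged. The stated completer expectation becomes about 19 instead of 20. The optional cap would limit panel choice for late enrollees.
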